7.2 Secondary Analysis

Based on the mITT data / Per Protocol data, at the 10-minute sample time, the efficacy targets for the Investigational Product are mean \log_{10} reductions from baseline skin flora counts ≥ 3 for the groin and ≥ 2 for the abdomen. At the 6-hour sample time, the efficacy targets are mean \log_{10} reductions from baseline that are greater than 0 for both groin and abdomen.

Log₁₀ reductions and responder rates will be compared between study materials. The Investigational Product and Active Control should demonstrate greater mean log₁₀ reductions from baseline at both 10 minutes and 6 hours and greater response rates at 10 minutes relative to the Vehicle Control.

7.3 Exploratory Analysis

Based on the mITT data / Per Protocol data, the weight (grams) of drug product solution applied to a treatment area will be compared between study materials for each body area from the product weight measured pre and post application.

7.4 Sample Size Justification

A sufficient number of volunteers will be enrolled in the screening phase such that the total numbers of evaluable samples collected from groin and abdominal regions are not less than 48 evaluable test sites from Investigational Product and Active Control and 16 evaluable test sites from the Vehicle Control arm arms (minimum of 112 each for groin and abdominal regions). Subjects must satisfy all Screening Day and Treatment Day Inclusion/Exclusion Criteria prior to screening sample collection and Treatment Day procedures. If the required numbers of subjects do not qualify from the initial screening group, additional volunteers will be recruited.

This is a Phase 2 study to assess the immediate and persistent antimicrobial effect of the Investigational Product relative to the log₁₀ reduction and response rate standards set forth in the Food and Drug Administration Tentative Final Monograph (TFM) for *Effectiveness Testing of a Patient Preoperative Skin Preparation* (FR 59:116, 17 June 94, pp. 31450-31452) and inform design of future Phase 3 pivotal efficacy studies. Therefore, no sample size calculation was performed to provide statistically-powered evidence of efficacy as part of this study. The sample size is deemed adequate for these purposes.

7.5 Safety Analysis

The full Intent to Treat data set (all randomized subjects) will be used for the safety analysis. The principal measures of safety will be skin irritation scores and the incidence of adverse events reported during the study.

Differences between the Investigational Product, Vehicle Control, and Active Control will be evaluated on skin irritation data.

7.6 **Study Flow Chart**

Procedure	Timeline (Days)			
	14 or more	2 on more prior	0	Treatment Day
	prior to Baseline	3 or more prior to Baseline	0 Baseline	3 or more post Baseline
Informed Consent Obtained	X			
Product-Restriction Period	X	X	X	
Inclusion/Exclusion Criteria including Medical History Reviewed	X	X	X	X
Clipping Hair From Test sites		X		
Baseline Screening			X	
Test-Day Baseline Sample		= 0,		X
Product Application				X
10-Minute Post-Product Application Sample				X
6-Hour Post-Product Application Sample				X
Adverse Events		X	X	X

Note: Visual evaluations of the skin on each test area will be performed at each laboratory visit prior to treatment, and prior to 10-minute and 6-hour post-treatment microbial sampling.

8.0 TEST MATERIALS

The test materials (Investigational Product, Vehicle Control and Active Control) to be used in this evaluation will be supplied by the study Sponsor. Treatment materials will be supplied in individually packaged pre-filled packs. The Investigational Product and Vehicle Control packs will be thermally treated to simulate a heat sterilization process to address any physical impact of heating on the cloth. Thermally treated cloths will not be tested for confirmation of sterility for use in this study.

The Investigational Product and Vehicle Control will be blinded. The Active Control cannot be blinded, due to package labeling of the marketed product. The test materials will be received and stored by BioScience Laboratories, Inc. (BSLI) in accordance with instructions from the Sponsor and retained in secure quarantine when not being used in testing. BSLI will maintain an inventory of the test materials in secure quarantine and a log of use. Unused, sealed test materials will be stored by BSLI until the Sponsor specifies its disposition. In the absence of a disposition request from the Sponsor within 1 year of planned usage, the test materials will be returned to the Sponsor. No test materials will be destroyed unless requested by the Sponsor. Lot Numbers and

Expiration dates will be provided by the Sponsor with each product shipment. The unblinded lot numbers of the Investigational Product and Vehicle Control will be provided to BSLI by the Sponsor at the completion of the study when unblinding has occurred.

Investigational Product (IP):	Thermally treated polyester A&W5 Cloths Impregnated with 0.4% w/v Octenidine Dihydrochloride (OCT) Aqueous Solution
Active Ingredient:	0.4% w/v Octenidine Dihydrochloride (OCT) Aqueous Solution
Lot Number:	E
Expiration Date:)
Vehicle Control (VC):	Thermally treated polyester A&W5 Cloths Impregnated with Vehicle Formulation
Active Ingredient:	Not applicable
Lot Number:	
Expiration Date:	
Active Control (AC):	Sage 2% Chlorhexidine Gluconate Cloth
Active Ingredient:	2% Chlorhexidine Gluconate (CHG)
Lot Number:	
Expiration Date:	
LABORATORY SUPPLIE Laboratories, Inc.)	CS AND EQUIPMENT (provided by BioScience
Equipment	
	this study will be detailed on Clinical Trials Equipment ms will be included in the Final Report.
Supplies	
	s study will be detailed on Clinical Trials Supplies Tracking included in the Final Report.
Media	

9.0

9.1

9.2

9.3

Sterile Sampling Solution (SS):

BSLI PROTOCOL #1608374-103 / BD PROTOCOL MPS-16IPVAW01
Page 14 of 46
BIOSCIENCE LABORATORIES, INC.

Butterfield's Phosphate Buffered Water (PBW):

312 μ M KH₂PO₄, pH 7.2 \pm 0.1

Tryptic Soy Agar with product neutralizers (TSA+) - may be purchased or made by BSLI

NEUTRALIZATION 10.0

A neutralization study will be performed to ensure that the neutralizers used in the recovery medium quench the antimicrobial activity of the three test materials, and that the neutralizers are not toxic to the bacteria. Staphylococcus epidermidis (ATCC #12228) and Staphylococcus epidermidis MRSE (ATCC #51625) will be used as the challenge species in the neutralizer study. The neutralization study will follow guidelines based on ASTM E1054-08(2013), Standard Test Methods for Evaluation of Inactivators of Antimicrobial Agents. Reference Appendix 3 of this Protocol for specific guidelines for the Neutralization Assay. The neutralization validation will be completed prior to initiation of the clinical investigation and results will be documented in the Final Report.

11.0 SUBJECT SELECTION

11.1 **Number of Subjects**

A sufficient number of male and female, overtly healthy volunteer subjects at least 18 years of age, will be enrolled in the screening phase to ensure that the total numbers of evaluable samples collected from groin and abdominal regions are not less than 48 evaluable test sites from Investigational Product and Active Control arms and 16 evaluable test sites from Vehicle Control arm (minimum of 112 each for groin and abdominal regions). A minimum of 56 evaluable subjects is required to achieve a total of at least 112 test sites for groin and abdominal regions. Subjects must satisfy all Screening Day and Treatment Day Inclusion/Exclusion Criteria prior to screening sample collection and Treatment Day procedures. If the required numbers of subjects do not qualify from the initial screening group, additional volunteers will be recruited.

Subject Recruitment 11.2

Following approval of the Study Protocol, Informed Consent Form, and other study specific documents by the GIRB and Sponsor, potential subjects will be recruited. Personal information will be collected for each potential subject, using the Subject Confidential Information and Acceptance Criteria Form (SCIAC form, Form No. 15-SR-004). Each consenting subject will fill out an Informed Consent Form (ICF) and the Authorization to Use and Disclose Protected Health Information Form (HIPAA form, Form No. 15-SR-008). A List of Restricted Products will be provided to each subject prior to beginning the study. The above forms are provided as separate Informed Consent documents. During the consenting process, emergency contact information of individuals who can be contacted, should any problem arise, will be collected for each

participant. Trained personnel or subject recruiters will explain the study to each subject, review the elements of Informed Consent as specified in 21 CFR 50.25, and determine subject eligibility through direct questioning, and will be available to answer any questions that may arise. It will be made clear to subjects that their participation in this study will accrue to them no personal benefits, other than financial compensation, as stated. The Informed Consent Form will be signed and dated by the subject and the person obtaining consent prior to the start of any study procedures. The subject will receive a copy of the signed Informed Consent Form. Subjects will be notified that additional information about this study can be found at www.clinicaltrials.gov.

The subject recruiters will verbally verify with subjects that the skin of the abdomen and inguen are free from clinically evident dermatoses, injuries, or any other disorders that may compromise the subject or the study.

Potential subjects will be informed of volunteer opportunities available at the investigative site by means of general, nonspecific newspaper and radio advertisements instructing potential subjects to either read GIRB-approved study descriptions online at www.biosciencelabs.com or in person at BioScience Laboratories, Inc., Subject Recruitment Office. Additionally, subjects may be recruited from existing subject database, referrals, through response to advertising and from community outreach and events. All study-specific advertising materials will be approved by the GIRB prior to their use for recruiting subjects.

11.3 Criteria for Inclusion

Potential subjects may be included in this study if they meet the following requirements:

- Subjects may be of either sex, at least 18 years of age and of any race.
- Subjects must be in good general health.
- Subjects must read and sign an Informed Consent Form, Authorization to Use and Disclose Protected Health Information Form, and List of Restricted Products prior to participating in the study.
- Female subjects must have a negative urine pregnancy test documented before treatment with test materials.
- Screening day microbial baseline requirements for subjects of ≥ 3.11 log₁₀ CFU/cm² bilaterally from the skin of the abdomen and $\geq 5.50 \log_{10} \text{CFU/cm}^2$ bilaterally from the skin of the groin.

Criteria for Exclusion: Medical History/Status Ascertained from Direct Questioning 11.4 of a Prospective Subject

Potential subjects will be excluded from participation if any of the following criteria apply to them.

- Known allergies or sensitivities to sunscreens, deodorants, laundry detergents, fragrances, vinyl, latex (rubber), alcohols, metals, inks, or to common antibacterial agents found in soaps, lotions, or ointments, particularly chlorhexidine gluconate (CHG), or octenidine dihydrochloride (OCT).
- Exposure of test sites to strong detergents, solvents, or other irritants within the 14-day product-restriction period or during the test period.
- Exposure of test sites to antimicrobial agents, medicated soaps, medicated shampoos, or medicated lotions, use of biocide-treated pools or hot tubs, use of tanning beds, or sunbathing during the 14-day product-restriction period or during the test period.
- Wear fabric softener-treated clothing (including bug-repellent and UV-treated clothing) during the 14-day product-restriction period or during the test period.
- Use of systemic or topical antibiotic medications, steroid medications (other than for hormonal contraception or post-menopausal reasons), or any other product known to affect the normal microbial flora of the skin during the 14-day product-restriction period or during the test period.
- A medical diagnosis of a physical condition, such as a current or recent severe illness, mitral valve prolapse with a heart murmur, congenital heart disease, hepatitis B, hepatitis C, an organ transplant, or an immunocompromised condition such as AIDS (or HIV positive), lupus, diabetes, Crohn's disease, asthma or medicated multiple sclerosis.
- Any tattoos, or scars within 2 inches of the test sites; skin blemishes or warts, may be permissible with the specific approval of the Principal Investigator or Consulting Physician.
- Dermatoses, cuts, lesions, active skin rashes, scabs, breaks in the skin or other skin disorders within 6 inches on or around the test sites.
- A currently active skin disease or inflammatory skin condition (for example, contact dermatitis, psoriasis, eczema) anywhere on the body that, in the opinion of the Principal Investigator, would compromise subject safety or study integrity.
- Subjects who receive an irritation score of 1 (any redness, swelling, rash, or dryness present at any treatment area) for any individual skin condition prior to the Screening Day baseline or Treatment Day baseline sample collection.
- Participation in another clinical study in the past 30 days or current participation in another clinical study.
- Showering, bathing, or swimming within the 72 hour period prior to sampling for baseline screening, the test day, or throughout the test period.

- Pregnancy, plans to become pregnant or impregnate a sexual partner within the pretest and test periods of the study, or nursing a child. All female subjects will be required to complete a urine pregnancy test on the day of test material application, prior to treatment. Both gender of subjects must be willing to use an acceptable method of contraception to prevent pregnancy for at least 14 days immediately preceding Treatment Day and throughout the duration of the study.
- Any medical condition or use of any medications that, in the opinion of the Principal Investigator or Consulting Physician, would preclude participation.
- Unwillingness to fulfill the performance requirements of the study.

SUBJECT WITHDRAWAL 12.0

After admission to the study, the subject may withdraw at any time for any reason. If possible, the reason for withdrawal will be recorded. Any subject not adhering to Protocol requirements will be disqualified. At the discretion of the Principal Investigator, subjects will be allowed to make a maximum of two attempts at achieving baseline bacterial counts to qualify for treatment day procedures. Subjects who have received product are not eligible to re-enter the study.

13.0 **PROCEDURES**

13.1 Compliance with Good Clinical Practices and Regulatory Requirements

The study will be conducted in compliance with the Good Clinical Practice regulations as required by the FDA, Good Laboratory Practice regulations as required by the FDA, the standard operating procedures of BSLI, the study protocol, and any protocol amendments, and the regulatory requirements of the FDA and ICH.

Subjects will be questioned prior to and during the study to ensure compliance with study requirements.

13.2 **Product Restriction Period**

The 14-day period prior to the baseline-screening portion of the study will be designated the "product restriction" period. During this time, subjects will avoid the use of medicated soaps, lotions, shampoos, deodorants, etc., as well as skin contact with solvents, acids, and bases. Subjects will also avoid sunbathing, using UV tanning beds or bathing in biocide-treated (e.g., chlorinated) pools and/or hot tubs. Subjects will be provided a kit containing products that they will be instructed to use exclusively for personal hygiene during the course of the study.

Subjects must not remove hair from the anatomical sites to be treated from the beginning of the product restriction period until after the testing has been completed. The subjects will be instructed not to bathe or shower during the minimum 72-hour period prior their baseline screening procedures and completion of treatment day procedures. This regimen will allow for the stabilization of the normal microbial flora of the skin.

During the latter portion of the product-restriction period (at least 72 hours prior to the screening baseline procedures), subjects will be examined physically to ensure that there is no evidence of injury, dermatosis, or dermatitis present at the sampling sites. Any hair present on test areas will be clipped to ensure the comfort of the subject during sampling procedures, to ensure that bandages used in testing will remain secure to the test sites, and remove any variables in the test system.

13.3 Randomization

Subjects will be randomized to treatment using the following block design:

Treatment Balance

Each subject will receive two different treatments, one on the right side of the body and one on the left. This means there are three possible combinations of treatments (assuming A and B are either Investigational Product or Active Control; C is Vehicle Control):

- A and B
- A and C
- B and C

The treatment assignments will be balanced such that the number of readings per anatomical site matches the calculated requirements. The Investigational Product and Active Control will be applied to an equal number of anatomical sites. The Vehicle Control will be compared against each active substance an equal number of times. The Vehicle Control will be applied to the number of anatomical sites necessary to generate a baseline for comparison to the active substances.

A minimum of 56 evaluable subjects will be required to achieve a total of at least 112 test sites for groin and abdominal regions. Out of the minimum 56 evaluable subjects, 40 evaluable subjects will receive treatments from both A and B, 8 evaluable subjects will receive treatments from both A and C and 8 evaluable subjects will receive treatments from both B and C to achieve 48 evaluable test sites from Investigational Product and Active Control arms (A and B) and 16 evaluable test sites from Vehicle Control arm (C) for groin and abdominal regions.

Left/Right Balance

The application will be randomized so that each treatment is used on an equal number of left and right sides of the body.

Site and Sample Time Balance

Each groin and abdomen sample site is divided into four areas and three of the areas will be sampled – one at baseline, one at 10 minutes, and one at 6 hours. The remaining area will not be used. Therefore, for any groin or abdomen site there are 24 possible sampling orders.

The number of subjects required for a completely balanced block design for all factors at once is dependent on the ratio of the number of anatomical sites used in the active treatments compared to the number of anatomical sites used in the Vehicle Control treatment but is in any case a multiple of 48 (a factor of two for left/right balance times a factor of 24 for sample order balance). The exact subject numbers and Active/Vehicle Control ratio may make it infeasible to provide a completely balanced block design, so the following priority order will be used for design:

- 1. Treatment combinations will always be applied in balanced blocks, with the block size being sufficient to preserve the active to active ratio at 1:1 and to preserve the active to Vehicle Control treatment ratio as determined by the Investigator and statistical consultant.
- 2. Left/right balance will be preserved each treatment will be applied an equal number of times to each side of the body.
- 3. Sampling orders will be assigned in blocks of 24 as much as possible. If the final number of subjects is not a multiple of 24 the remaining subjects will be assigned random non-duplicate sample orders from the 24 possible sample orders.
- 4. The blocking will be adjusted based on the final subject numbers to be as balanced as possible with respect to all three factors at once, with priority using the order listed above.

13.4 **Clipping Procedures**

At least 3 days (72 hours) prior to baseline screening procedures, the subjects will be examined physically to ensure that there is no evidence of injury, dermatosis, or dermatitis present on the test areas. Any hair present on test areas will be clipped to remove any test variables between subjects, to ensure that bandages used in testing will remain secure to the test sites and ensure the comfort of the subject during sampling Subjects will be encouraged to shower after clipping to decrease the incidence of folliculitis.

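### Section 13.3 balances the 24 sampling orders over all subjects and leaves Vehicle area-by-time balance to chance; Latin-square sets of four would give it exactly at the planned 56 subjects

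*Combined protocol and SAP*

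**What the plan says.** All of this is in protocol Section 13.3.

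- **Treatments.** Each subject receives two products, one per side: "40 evaluable subjects will receive treatments from both A and B, 8 evaluable subjects will receive treatments from both A and C", and 8 more receive B and C. This gives "48 evaluable test sites from Investigational Product and Active Control arms (A and B) and 16 evaluable test sites from Vehicle Control arm (C" for each region. The 56 subjects are a minimum: "A minimum of 56 evaluable subjects will be required to achieve a total of at least 112 test sites for groin and abdominal regions".
- **Sides.** "The application will be randomized so that each treatment is used on an equal number of left and right sides of the body".
- **Areas.** "Each groin and abdomen sample site is divided into four areas and three of the areas will be sampled", one each at baseline, 10 minutes and 6 hours, so that "for any groin or abdomen site there are 24 possible sampling orders".
- **Complete balance.** The required number depends on the ratio of active to Vehicle sites and "is in any case a multiple of 48 (a factor of two for left/right balance times a factor of 24 for sample order balance". The section accepts that this may not be feasible and gives a priority list.
- **Priority list.** Rule 1 protects the treatment combinations and rule 2 the left/right balance. Rule 3 reads "Sampling orders will be assigned in blocks of 24 as much as possible", with random non-repeated orders for any remainder. Rule 4 asks for the best joint balance on all three factors, in that order of priority.

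No rule states how often each area should serve each time point within a product.

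**The concern.** Sections 7.1 and 15.1 define a log reduction as the Treatment Day baseline recovery minus the post-application recovery. The two counts come from different areas of the same site. If flora density differs systematically between areas, a product whose baselines fall mostly in the denser areas will appear to reduce counts more.

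What cancels this in a product's mean is equal use of each area at each time point. That needs four orders forming a Latin square, not all 24. By aiming at 24 orders, the section sets a target that the planned size cannot meet and passes over one that it can.

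Vehicle is most exposed because it has only 16 sites. It is the reference for the secondary goals in Sections 7.2 and 15.2 that both actives outperform Vehicle. The two-proportion test and simple responder rates named there carry no adjustment for area.

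**Working it through.** **The plan's figures.** Orders: 4 × 3 × 2 = 24. Sides times orders: 2 × 24 = 48. Sites: A = 40 + 8 = 48, B = 40 + 8 = 48, Vehicle = 8 + 8 = 16; total 112 = 2 × 56. All reproduce.

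**What 24-order balance needs at 40/8/8 (5:1:1).**
- Crossing pair, side and order: 7 × 2 × 24 = 336 subjects.
- Balance by product and side only: Vehicle has N/7 sites per side, which must be a multiple of 24, so N = 168.
- The plan has 56 = 2 × 24 + 8, a multiple of neither 24 nor 48.

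**What area-by-time balance needs.** The 24 orders split into six 4 × 4 Latin squares. With each pair split evenly over sides, the pair-by-side cells are 20, 20, 4, 4, 4 and 4. All are multiples of 4, so 14 squares fill them: 14 × 4 = 56. In a list built this way, every area serves every time point 6 times per side for A and for B (24 sites per side), and 2 times per side for Vehicle (8 per side). It uses 16 orders twice and 8 orders three times (16 × 2 + 8 × 3 = 56). That is two full sets of 24 plus 8 distinct orders, so it is compatible with rules 1 to 3.

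**What the present rules give Vehicle.** Let tau be the SD (divisor 4) of the true mean log10 counts over the four areas. The difference between two distinct randomly chosen areas has variance 2 tau² + (2/3) tau² = (8/3) tau². For n sites whose orders are drawn without replacement from a balanced set of M, the area part of the mean log reduction has variance (8/3) tau²/n × (M − n)/(M − 1).

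- *Rule 3 alone* (two blocks of 24 plus 8 distinct orders, drawn independently of treatment, same order on both sides). With M = 56 and n = 16: (8/3)/16 × 40/55 = 0.121, SD 0.35 tau. The 8 leftover orders are not themselves balanced, and simulation gives about 0.36 tau. Vehicle baselines are 4/4/4/4 in about 2% of lists, and one area supplies 7 or more of the 16 in 21%. Balance at all three times together occurred in at most 0.005% of 100,000 lists.
- *Rule 4 used to give Vehicle 16 distinct orders.* With M = 24: (8/3)/16 × 8/23 = 0.058, SD 0.24 tau. Baselines are 4/4/4/4 in about 7%. No area can supply more than 6, because each area is the baseline area in only 6 of the 24 orders.

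**Size.** The documents give neither tau nor a site SD. Assume tau = 0.1, 0.2 or 0.3 and a site SD of 0.8, so the variance of the Vehicle mean is 0.8²/16 = 0.04. The relative increase is (k tau)²/0.04.

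| | tau 0.1 | tau 0.2 | tau 0.3 |
|---|---|---|---|
| Rule 3 alone, k = 0.36 | 3% | 13% | 29% |
| 16 distinct orders, k = 0.24 | 1.4% | 6% | 13% |

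The first row is like having 16/1.03 = 15.5, 16/1.13 = 14.2 or 16/1.29 = 12.4 Vehicle sites. If the two sides draw separate orders, k is about 0.38, or 32% at tau 0.3.

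For the Investigational Product (48 sites), k is about 0.11. At tau 0.3 the standard error goes from √(0.8²/48) = 0.115 to √(0.0133 + 0.033²) = 0.120. With separate orders per side, k is about 0.19 and it reaches √(0.0133 + 0.057²) = 0.129.

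**The case against.** The strongest reply is that rule 4 already asks for the best joint balance and that the Latin-square list is compatible with rules 1 to 3. A careful statistician could produce it under the present text. A simulation of rule 3 alone describes someone who ignores rule 4. This stands in part. A reader might infer that the plan forces the Vehicle sites to be unbalanced, and the text does not support that. But rule 4 names no area-by-time target, and an obvious way to apply it, 16 distinct orders for Vehicle, still gives 4/4/4/4 baselines in only about 7% of lists.

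A reader might also infer that Vehicle results would be biased. They would not. Areas are assigned at random (Sections 7.0 and 13.6), so the area contribution averages zero over lists and only adds variance. The log-reduction comparison uses a mixed model, and Section 15.0 leaves details to a separate analysis plan.

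A third reading is that the section gives up balance only below 48 subjects. The condition is a multiple of 48, together with the treatment ratio; 56 exceeds 48 and fails because it is not a multiple.

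Two limits on the remedy also stand.
- Only area effects common to all subjects are removed. Patchiness peculiar to one subject is not.
- Exact balance belongs to the randomised list. Sites leave the mITT set on Treatment Day baseline counts (Section 7.1), and subjects may qualify for one region only (Section 13.5). By the formula above, randomly losing 2 of 16 balanced Vehicle sites leaves √[(8/3)/14 × 2/15] = 0.16 tau. Randomising 20 and losing 4 leaves √[(8/3)/16 × 4/19] = 0.19 tau.

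**Conclusion.** The point holds as an avoidable loss of precision. Section 13.3 balances a finer unit than the endpoint requires, cannot reach that balance at 56 subjects, and leaves Vehicle area-by-time use to chance. Under the assumed tau of 0.1 to 0.3 log10 and site SD of 0.8, the variance of the Vehicle mean rises by about 1.4% to 29%, depending on tau and on how rule 4 is applied. The low end is trivial. The consequence falls mainly on the secondary Vehicle comparisons. It would be too strong to say that the primary 70% responder target for the Investigational Product is compromised: with the same order on both sides, its standard error for mean log reduction moves only from 0.115 to 0.120 at the top of the range. Section 7.4 states that this Phase 2 study was not sized for powered evidence. The case for acting is that the better list costs almost nothing.

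**What to change.** In Section 13.3:

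1. State area-by-time balance within product and side as the target of rules 3 and 4.
2. Have rule 3 assign orders within each treatment-pair-by-side cell in sets of four forming a Latin square, so that in each set every area is used once for baseline, once for 10 minutes, once for 6 hours and once left unused. Rotate the six squares so that all 24 orders are used.
3. Limit the multiple-of-48 sentence to balance over all 24 orders. Add that area-by-time balance is exact for the randomised list at 40/8/8 = 56 subjects: each area 6 times per time point per side for each active, and 2 times for Vehicle.
4. Note that baseline exclusions and single-region entry may leave the analysed sites only approximately balanced. Letting a replacement subject take the order of the one replaced would limit this.

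The cost is a regenerated randomisation list and a few sentences. No subjects, samples or staff are added, and each order is still used two or three times.
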